1. CLINICAL PROTOCOL

1.1 Background

Recent studies have shown that inflammation plays an important role in the pathogenesis of Dry Eye Disease (DED). Ocular surface inflammation often exacerbates the subject's signs and symptoms, and results in an increase in the immune cells and other inflammatory mediators located in the ocular surface. Dry eye disease is one of the most commonly encountered ophthalmic disorders. It is a multifactorial disease of the ocular surface and tear film, characterized by symptoms of eye irritation, tear instability and vision impairment. Despite being very common, standardized therapy is not available.

Due to the underlying inflammation associated with DED, anti-inflammatory steroid medications are used for the treatment of DED. "Soft steroids" are often preferred because their chance of increasing intraocular pressure (IOP) is lower than other steroids. One of the "soft steroids" that is commonly used for the treatment of inflammation associated with ocular surface disease is loteprednol etabonate 0.5% ophthalmic suspension (Lotemax, Bausch & Lomb, Inc).

Current steroid therapy in DED is comprised of pulse therapy (to avoid adverse events associated with long-term steroid use) of usually 2 weeks duration, administered BID. This timeframe is often too short to meaningfully resolve the inflammation associated with DED. More recently steroid treatment of at least 6 weeks with tapered dosing has been advocated.

1.2 Rationale

Lotemax, an FDA-approved medication for ocular inflammatory disease, is commonly used to treat inflammation associated with DED with a regimen of twice daily for 2

weeks. However, because DED is a chronic disease, this short duration of steroid therapy may not be enough to meaningfully resolve the inflammation associated with DED. Thus, corneal specialists, including here at MEEI, have begun using Lotemax for at least 6 weeks with tapered dosing. This study has been designed to evaluate the effects of this tapering regimen on inflammation associated with DED.

Clinical signs and symptoms are used to evaluate the efficacy of a treatment for DED, including Schirmer's test, tear break-up test, corneal fluorescein staining, and conjunctival lissamine green staining. However, none of these tests evaluate the underlying inflammatory and immune response changes in DED. Therefore, to determine the efficacy of any treatment for DED, it is ideal to evaluate these underlying changes in addition to the clinical parameters.

In vivo confocal microscopy (IVCM) is a novel imaging technology that allows the visualization and quantification of corneal structures at the cellular level. IVCM has recently been used to evaluate the corneal changes in DED, such as hyperfluorescent superficial epithelial cells, immune dendritic cells, and sub-basal nerves.

Therefore, in this randomized clinical trial, IVCM images will be used to determine the changes in corneal immune cells and nerves during a 6-week taper regimen of Lotemax versus Soothe Tired Eyes Lubricant Eye Drop (Glycerin 1.0%, Bausch & Lomb Inc.) (an artificial tear) for treatment of inflammation associated with DED.

2. STUDY OBJECTIVES

2.1 Primary Objective

To evaluate the efficacy of Lotemax as compared to Artificial Tear over a period of 6 weeks, using clinical and in vivo confocal microscopic findings.

2.2 Secondary Objective(s)

N/A

3. STUDY DESIGN

3.1 Study Design Description

This is a single site, prospective, randomized, controlled, double-masked clinical trial including 50 subjects with DED. The participants will be randomized to take either Lotemax or Soothe Tired Eyes Lubricant Eye Drops for 6 weeks. Both Lotemax and the artificial tear will be used 4 times a day for 2 weeks, 2 times a day for 2 weeks, and once a day for 2 weeks. After screening/baseline examination and enrolling into the study, the participants will have follow-up visits at 2 weeks as well as 6 weeks.

3.2 Allocation to Treatment

The subjects will be randomized in two groups, one group will receive Lotemax and the other group will receive Soothe Tired Eye Lubricant Eye Drops.

3.2.1 Randomization Procedures

Once the investigator determines that the subject has met all of the inclusion and exclusion criteria, the subject will be randomized to take either Lotemax or Soothe Tired Eyes Lubricant Eye Drops (artificial tears). The randomization will be in a 1:1 ratio using a permuted-block design (which will be obtained using a computer-based random code generator) into the two groups.

3.2.2 Masking Procedures

The study drugs will be labeled by the Massachusetts Eye & Ear pharmacy with instructions for storage, the name of the study, an expiration date, and a notice that

the bottle may contain Lotemax. The pharmacy will maintain a master list of the participants' name, unique identifier, and the coded treatment assignment. The randomization scheme and treatment assignment will be held in the pharmacy to ensure that the investigator and study team remain masked. Participants, investigators, image analysts, and the sponsor (GSK) will be masked to the treatment group.

3.2.3 Breaking the Mask

A subject's medication may be unmasked at any point for a medical emergency or to supplement a serious adverse event (SAE) report. The subjects will be unmasked at the end of the study in order to provide optimal ongoing care.

4. SUBJECT SELECTION

4.1 Subject Inclusion Criteria

- Age 18-89 years.
- Willing and able to provide written informed consent.
- Willing and able to comply with study assessments for the full duration of the study.
- Diagnosis of dry eye disease based on the followings:
 - Symptoms of dry eye disease such as foreign body sensation, burning, stinging, light sensitivity for at least 6 months.
 - Two or more of the following objective signs:
 - Schirmer test with anesthesia <10 mm at 5 minutes [mean Schirmer between eyes.

- Tear break-up time (TBUT) of <10 seconds.
- Corneal fluorescein staining of 4 (NEI grading scheme, 0-15) in at least one eye
- Lissamine green staining of the nasal and temporal conjunctiva
 (NEI grading scheme, 0-18) in at least one eye
- Corneal dendritiform cell count by confocal microscopy of >=75/mm² (13 immune cells per image)
- In good stable overall health.

4.2 Subject Exclusion Criteria

- Central corneal subbasal dendritic cell count by *in vivo* confocal microscopy of
 <75/mm² in both eyes
- Active ocular allergies
- Active allergies to steroids, aminoglycosides, or benzalkonium chloride (BAK)
- History of contact lens wear within 3 months before enrollment.
- Intraocular surgery or ocular laser surgery within 3 months before enrollment.
- History of ocular infection within 3 months before enrollment.
- History of topical or systemic steroid treatment within 1 month before enrollment. In case of topical steroid use, a wash-out period of 1 month is required.
- History of increased intraocular pressure after using topical steroids (steroid responsive)

- History of systemic immunosuppressive treatment within 1 month before enrollment.
- History of any change in the frequency of topical cyclosporine or oral tetracycline compounds (tetracycline, doxycycline, and minocycline) within 1 month before enrollment.
- Any condition (including language barrier) that precludes subject's ability to comply with study requirements including completion of study.

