7. STUDY PROCEDURES

7.1 Screening Procedures

Prospective participants, as defined by the inclusion/exclusion criteria, will be considered for entry into this study. Concurrent enrollment of subjects who are participants in other studies will be allowed based on the investigator's discretion.

During the consent process, study design and treatment regimen will be discussed with each subject. Written informed consent will be obtained before any study specific procedures are performed. However, standard of care clinical information (such as: medical history, TBUT, staining, and Schirmer's test) obtained during a subject's clinical visit within the previous 48 hours can be used during the screening visit to determine eligibility and as their baseline assessments. Additionally, standard of care IVCM images taken within a week of, or during, the subject's screening visit may be used to determine eligibility and as a baseline assessment.

The following evaluations and procedures will be performed for all subjects during the screening and baseline period:

- Written informed consent
- · Record of current ocular and systemic medications
- Record of significant medical/surgical history in the past 5 years
- · Record of demographic data, including date of birth, sex, and race/ethnicity
- Tear Break-up Time (TBUT)
- Eye examination (best corrected visual acuity, slit lamp biomicroscopy, applanation tonometry, funduscopy)
- · Corneal fluorescein staining
- · Conjunctival lissamine green staining

- · Schirmer's test with anesthesia
- · Central corneal in vivo confocal microscopy (IVCM)

Researchers will document type and frequency of artificial tear, ocular ointment, and other dry eye therapies use by the subject.

Subjects will start the study medication the first day after their screening visit, while continuing the use of their current medications.

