7.8 Schedule of Activities (Study Table)

Т	able1- Schedule	e of events ar	ıd procedu	res	
Visit#	1			2	3
Visit Description	Screening	Baseline	Day 1	Week 2	Week 6 (±
				(± 3 days)	1 week)
Obtain Informed Consent	X				
Inclusion/ exclusion criteria	X				
Medical and Ophthalmic History	X		START OF STUDY MEDICATION	X	X
Medication History	X		DICA		
BCVA	X		Y ME	X	X
OSDI		X	IUD	X	X
SANDE		X	OF S	X	X
TBUT	X		ART	X	X
Biomicroscopy	X		ST	X	X
Corneal staining	X			X	X
Schirmer with anesthesia	X			X	X
Conjunctival staining	X			X	X

Intraocular Pressure	X		X	X
Funduscopy	X		X	X
In vivo confocal	X		X	X
microscopy				
Concommitant			X	X
medications				
Compliance and	X	X	X	X
adverse events check				

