10.6 Safety Analysis

The primary safety variable monitored will be the occurrence of adverse events. The severity of each adverse event observed will be evaluated as serious or not serious as defined by the MEEI HSC and the occurrence will be evaluated as expected or unexpected. The relationship of the event to the study medication will be assessed by the investigator as possibly, probably, or definitely related. Safety variables will be evaluated at screening and at all study visits. If adverse events occur, the first concern will be the safety of the study participants. Any serious adverse event occurring

during the study period will be immediately reported to MEEI IRB. Directed questioning (Ocular Tolerability and Compliance Questionnaire – Appendix I) and examination will then be done to assess tolerability. These questions are used to assess common and expected symptoms related to instillation or use of the study eye drops. Subjects will be asked to rate their symptoms from trace to severe.

Additional steps taken to assess safety will be followed as outlined in section 8.1 of this SUPP M form.

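### Eligibility has no glaucoma, ocular hypertension or screening-IOP limit, so a steroid-naive subject with any of these may be randomised, with a 1-in-2 chance of up to 6 weeks of bilateral loteprednol

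*Combined protocol and SAP*

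**What the plan says.** Section 4.2 has one criterion that concerns eye pressure: "History of increased intraocular pressure after using topical steroids (steroid responsive". Two other criteria are general. Section 4.1 asks for good, stable overall health, and 4.2 ends with a catch-all for conditions that would stop a subject complying with or completing the study.

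Section 3.2.1 makes the listed criteria the gateway to allocation: "Once the investigator determines that the subject has met all of the inclusion and exclusion criteria, the subject will be randomized", in a 1:1 ratio. Section 7.1 is a little softer: "Prospective participants, as defined by the inclusion/exclusion criteria, will be considered for entry into this study".

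The information needed to judge pressure risk is collected before allocation. Section 7.1 lists "Eye examination (best corrected visual acuity, slit lamp biomicroscopy, applanation tonometry, funduscopy", current ocular and systemic medications, and "Record of significant medical/surgical history in the past 5 years". The table in 7.8 has a screening entry for "Medical and Ophthalmic History" and another for intraocular pressure. Section 10.6 adds: "Safety variables will be evaluated at screening and at all study visits". Dosing follows at once: "Subjects will start the study medication the first day after their screening visit". Under 5.1 both eyes are treated for 6 weeks on a reducing schedule.

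The plan recognises a pressure rise as a risk of the study steroid. Section 5.1 describes corticosteroids as able to raise IOP, with a smaller effect for loteprednol, and provides a rapid taper and stop within 1 week if Lotemax raises the pressure. Section 11.1 collates pressure-related adverse events. Section 13.2 lists, as a possible reason to discontinue the study, 50% of subjects having a rise that takes IOP above 30.

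**The concern.** The plan names the hazard but screens only for people in whom it has already appeared. Someone who has never had a topical steroid has had no chance to show a steroid response, so the one pressure criterion cannot exclude that person, whatever the diagnosis or the reading on the day.

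What is at stake is avoidable exposure of identifiable subjects. A subject who enters with raised IOP has less margin before a further rise matters. That a subject with known glaucoma tolerates a rise less well is a clinical premise; the documents give no figure for it.

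There is a smaller possible cost in data. Section 5.2 keeps concomitant regimens constant and lets the investigator withdraw a subject whose regimen must change. Section 7.7 adds no procedures after withdrawal. A treated subject whose pressure medication had to be changed could therefore lose later outcome data, although adverse events are followed to resolution (8.1, 9.3).

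**Working it through.** No sample size, power or alpha figure bears on this point, so there is no plan figure to reproduce. The check is a reading of every criterion and safeguard against one test case: a steroid-naive subject with known glaucoma, ocular hypertension or a raised screening IOP.

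**Step 1. Count the entry criteria that address pressure (4.1, 4.2).**
- Prior IOP rise on topical steroids: 1
- Glaucoma: 0
- Ocular hypertension: 0
- Screening-IOP threshold: 0

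Neither glaucoma nor ocular hypertension is mentioned anywhere else in the document. Some staining thresholds in 4.1 look damaged by text extraction, but nothing suggests that a pressure criterion was lost.

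**Step 2. Apply the criteria and the discretion clauses to the test case.**

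| Provision | Does it exclude the test case? |
|---|---|
| Prior steroid response (4.2) | No; it cannot be met without earlier steroid use |
| Good overall health (4.1) | Possibly, if an investigator applies it to poorly controlled disease; it defines no ocular condition |
| Compliance catch-all (4.2) | Possibly, if pressure treatment is expected to need changing (5.2); it is not a safety or pressure limit |
| Consideration for entry (7.1) and safety evaluation at screening (10.6) | Discretion only; no value or diagnosis is named |
| Best-interest withdrawal (8.1, 9.3) | Discretion only; worded for continuing participation |

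Controlled glaucoma with a normal reading is the case least likely to be stopped by any row.

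**Step 3. Look at what happens after entry.**
- Allocation is 1:1, so the chance of loteprednol is 1/(1 + 1) = 1/2. If k such subjects enter, k/2 are expected to receive it. The documents give no basis for k.
- IOP is rechecked at weeks 2 and 6 (7.5, 7.8).
- The 5.1 taper protects the individual, but it has no numeric trigger and calls for a rise due to Lotemax while the investigator is masked (3.2.2). Unmasking through the pharmacy is available for that judgement (11.1).
- The 13.2 condition works at study level. Assuming all 50 subjects are the denominator, it needs 0.50 × 50 = 25 subjects. Under exact 1:1 allocation that is 50/2 = 25, the whole of one arm. It is not an individual safeguard.

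**Step 4. Ask whether the screening measurement itself is at fault.** It is not. IOP is a secondary outcome (10.2), so the screening reading has a use as baseline. The gap is that no entry rule refers to it.

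**The case against.** The strongest reply is that a corneal specialist sees the pressure, the fundus and the history before randomisation and would be unlikely to enrol someone at clear risk. The general-health criterion and the compliance catch-all give that specialist written grounds in some cases, and 7.1 says only that suitable people are considered. Loteprednol is described as having less effect on pressure than other corticosteroids (5.1), its frequency falls after week 2, and section 1.2 says that the site's specialists already use it for at least 6 weeks. This stands in part: discretion probably removes some subjects, mainly those with uncontrolled pressure. It does not supply a limit, and it leaves the decision to case-by-case judgement.

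Two stronger readings are tempting, and the documents do not support them:
- A reader might infer that such a subject is bound to receive 6 weeks of steroid. Entry leads only to a 1-in-2 chance, and 5.1 stops the drug early if Lotemax raises the pressure.
- A reader might size the problem by the interval between the week 2 and week 6 pressure checks. That interval applies to every subject on Lotemax, and the proposed exclusion would not change it. It describes monitoring frequency, not the eligibility gap.

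It is also fair to say that excluding controlled glaucoma is a choice; the documents do not show that this group must be kept out.

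**Conclusion.** The point holds as a gap in the entry criteria and should be fixed. Following the plan as written, a steroid-naive subject with known glaucoma, ocular hypertension or a raised screening IOP may be randomised, with a 1-in-2 chance of up to 6 weeks of bilateral loteprednol, subject to the 5.1 taper. The absence of a criterion is certain from the text. How often it would matter is unknown, because the number of such subjects cannot be derived from the documents.

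The conclusion rests on two things: the plan's own treatment of pressure as a steroid risk (4.2, 5.1, 11.1, 13.2), and the clinical premise that raised pressure or glaucoma leaves less tolerance for a further rise. It is a matter of patient safety. It does not call the choice or analysis of the primary endpoints into question.

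**What to change.** Add one exclusion to section 4.2: *Known glaucoma or ocular hypertension, or screening IOP in either eye above a numeric ceiling fixed by the sponsor-investigator before enrolment.*

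Both parts are needed. The diagnosis catches subjects whose reading is normal because they are already treated; 5.5 keeps existing medications constant, and the only medications it names as prohibited are other ophthalmic steroids. The ceiling catches raised pressure that nobody has diagnosed. The documents give no basis for a particular ceiling, so the sponsor-investigator must choose it. Because 7.1 limits the record of significant history to 5 years, the diagnosis should be asked about without a time limit.

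This is a cheap improvement. Ophthalmic history, tonometry and funduscopy are already obtained at screening, so no new procedure is needed. The exclusion acts before randomisation, so the target of 50 is unchanged. The downside is that a few otherwise eligible subjects are lost at screening and the population becomes slightly narrower, including the loss of subjects with controlled glaucoma.

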5.2 Study Drug/Device Compliance/Adherence

Directed questioning using the (Ocular Tolerability and Compliance Questionnaire – Appendix I) will be administered by the investigator or research staff. Results on the participants' compliance and adherence to the study protocol and study drug will be recorded on the paper case report form (CRF) at the second and third visits (2 and 6 weeks after enrollment).

Subjects will not be withdrawn for lack of compliance with the study drug regimen.

During the study, all concomitant medication treatment regimens, ocular hygiene treatments (i.e., lid scrubs and warm compresses), or insertion of punctal plugs will be kept constant as permitted by accepted medical practice. If one of the aforementioned treatment regimens needs to be modified, the participant may be withdrawn based on the investigator's discretion.

Additionally, if there is an administration of a prohibited medication (including any other steroid) or procedure (any ocular surgery), the participant may be withdrawn based on the investigator's discretion.

Participants must be compliant with IVCM imaging on at least 2 of their 3 visits or they will be withdrawn. Subjects who are withdrawn may be replaced by new enrolled subjects to maintain the sample size in each group.

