5.5 Other Medications

Administration

The use of any concurrent, prescription, or over-the-counter medication, is to be recorded along with the reason the medication was taken. During the study, all concomitant medication treatment regimens, ocular hygiene treatments (i.e., lid scrubs and warm compresses), or insertion of punctal plugs will be kept as constant as permitted by accepted medical practice.

Using artificial tears (preserved and non-preserved) are permissible at the screening visits and during the study. However, concomitant use of artificial tears will be monitored. At each study visit, subjects will be queried about the average number of times they used artificial tears each day during the past week and the number of days during the past week when they did not use any artificial tears.

Systemic and topical ophthalmic medications, that the subjects are already taking as part of their current treatment for dry eye disease will be maintained, without a change in frequency.

When necessary, treatment and administration of any other therapy, besides their current and study's regimen, will be done as the safety of the study participant is the primary consideration. The administration of a prohibited medication or procedure will be considered a protocol violation and the subject may be discontinued from the study. Prohibited medications include other ophthalmic steroids. Prohibited procedures include any ocular surgery.

• Rescue Medication or Therapy

When necessary, administration of any other therapy besides the study medication and their current medications will occur for the safety of the subject, which is the primary concern. If treatment with artificial tears is inadequate, or if the subject develops a severe form of ocular surface disease and dry eye, the subject may be unmasked by the investigator. To ensure the subject's safety and proper treatment, unmasking of the study treatment assignment will allow the investigator to institute appropriate follow-up care. The subject will be kept in the study so that we can do an "intention to treat" analysis.

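### Exclusion windows in 4.2 run back from enrolment, but 7.1 lets baseline tests be up to a week older, so a baseline image can fall inside a washout or precede a new dry-eye treatment.

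*Combined protocol and SAP*

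**What the plan says.** Section 4.2 ties its dated exclusions to enrolment. The one-month exclusions are "History of topical or systemic steroid treatment within 1 month before enrollment", "History of systemic immunosuppressive treatment within 1 month before enrollment" and, over the same period, "History of any change in the frequency of topical cyclosporine or oral tetracycline compounds". It adds "In case of topical steroid use, a wash-out period of 1 month is required", and gives that washout no separate end date. Contact lens wear, intraocular or laser surgery, and ocular infection each carry a three-month window.

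Section 7.1 uses a different clock for the measurements. Routine clinical information (medical history, TBUT, staining and Schirmer) "obtained during a subject's clinical visit within the previous 48 hours can be used during the screening visit to determine eligibility" and may also stand as baseline. A routine IVCM image from within a week of screening may serve both purposes too. Study drug starts the day after screening, with existing medication continued.

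Background treatment is controlled only once the subject is in the study. Section 5.2 covers concomitant regimens and lid hygiene, and ends its list with "insertion of punctal plugs will be kept constant as permitted by accepted medical practice". Section 5.5 says "Systemic and topical ophthalmic medications, that the subjects are already taking as part of their current treatment for dry eye disease will be maintained", at unchanged frequency. Neither section sets a minimum period before entry. Section 5.5 allows artificial tears throughout and monitors their use. Section 7.1 asks for the type and frequency of dry-eye therapies, but not when they were started or last changed.

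**The concern.** A washout protects a baseline only if it is complete when the baseline is measured. Here it need be complete only at enrolment, and the measurement may be older. The longest allowance, one week, applies to IVCM, which supplies all the primary endpoints in Section 10.1 and decides the 75/mm² criterion in Sections 4.1 and 4.2.

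Two things can go wrong with a reused test:

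- **Incomplete washout.** On the trial's own premise that the steroid reduces corneal inflammation, an image taken too soon after a steroid could show a lowered dendritic cell count. Later recovery would then be counted as change on study drug.
- **A treatment started after the test.** Baseline then precedes that treatment and weeks 2 and 6 follow it. The routine clinic visit that supplies the reusable measurement is also an ordinary occasion for changing treatment.

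At stake are the within-group changes in the primary endpoints, which Section 10.5 tests by ANOVA, and the correctness of entry decisions made on the image.

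**Working it through.** The plan states no figure for this gap, so there is none to reproduce. The check is date arithmetic, followed by a comparison of the sections.

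**Inputs**
- Washout in Section 4.2: one month, not given in days, so taken as 28 to 31 days.
- Oldest reusable IVCM image in Section 7.1: 7 days before screening.
- Oldest reusable clinical test in Section 7.1: 48 hours, or 2 days, before screening.
- Assumption: enrolment is on the day of screening. Section 7.2 allows baseline to follow screening immediately, and Section 7.1 starts study drug the next day.

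**Formulas.** Days off steroid at the baseline test = washout length − age of test. Shortfall = age of test ÷ washout length. Both are for a subject exactly one month off steroid at enrolment.

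| Month taken as | IVCM image | Shortfall | Clinical test | Shortfall |
|---|---|---|---|---|
| 28 days | 28 − 7 = 21 days | 7/28 = 25.0% | 28 − 2 = 26 days | 2/28 = 7.1% |
| 30 days | 30 − 7 = 23 days | 7/30 = 23.3% | 30 − 2 = 28 days | 2/30 = 6.7% |
| 31 days | 31 − 7 = 24 days | 7/31 = 22.6% | 31 − 2 = 29 days | 2/31 = 6.5% |

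The other one-month windows shorten in the same way. For a three-month window, taken as about 90 days, the largest shortfall is 7/90 = 7.8%.

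**What can start between a reused test and study drug.** Steroids and systemic immunosuppressants cannot, because the month before enrolment covers the whole gap. Nor can a changed cyclosporine or tetracycline regimen, if starting the drug counts as a change in frequency. Punctal plugs, lid scrubs, warm compresses, artificial tears, ointments and other dry-eye drugs can. No criterion in 4.2 mentions them, and Sections 5.2 and 5.5 apply only during the study.

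**Which results are touched**
- *Within-group change in the IVCM endpoints (10.5, ANOVA):* directly affected, because baseline is one of the values compared and there is no control to subtract.
- *Eligibility at 75/mm²:* affected, because the reused image may not represent the eye when study drug starts.
- *Between-arm comparison (10.5, Wilcoxon rank sum):* the text says that values are compared and does not say change scores. If follow-up values are compared, the date of the baseline test does not enter. If changes are compared, it adds noise.
- *OSDI and SANDE:* not among the reusable tests. Sections 7.2 and 7.8 place them at the baseline visit.

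**The case against.** The strongest objection is that a reader might infer from the suppressed-baseline argument that a true treatment effect will be masked. The documents do not support that for the randomised comparison. Allocation is 1:1 in permuted blocks and masked (3.2.1, 3.2.2), and follows the baseline assessments (7.2). A short washout or a new treatment is therefore as likely in one arm as in the other, and recovery would occur in the artificial-tear arm too. This part of the objection stands.

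The gap is also limited. Reuse is optional, 21 to 24 days is the extreme case, and clinical tests lose at most two days. A subject whose reused image shows fewer than 75/mm² in both eyes is excluded, so the most strongly suppressed images do not enter the analysis. The documents offer no evidence that plugs, lid care or tears begun within a week alter IVCM measures. Section 10.5 already plans to compare potential confounders between arms. These points limit the harm but do not close the gap: no section requires the washout to be complete, or treatment to be unchanged, on the date of the reused test.

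A reader might also infer that Section 4.2 must impose a month of stability on all dry-eye care. That does not follow. Section 5.5 deliberately permits and monitors artificial tears, and such a rule would trade recruitment against homogeneity on clinical grounds.

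**Conclusion.** The point holds as a limited and inexpensive correction. Sections 4.2 and 7.1 use different reference dates, so a reused baseline IVCM image can be up to 7 days, or 23 to 25%, short of the stated one-month washout. A reused clinical test can be up to 2 days, or 6 to 7%, short. Background treatments not named in 4.2 can begin inside the same gaps.

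The consequence is a contaminated baseline for the within-group ANOVA, a less reliable 75/mm² check, and added noise if the arms are compared on change from baseline. It is not a systematic bias between arms.

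The effect on the results cannot be computed. The documents do not say how many subjects will have recent steroid use, a recent treatment change or a reused test, nor how fast dendritic cell density recovers. A reader might infer a particular number of affected subjects, or a particular imbalance among the 50, but nothing in the documents supports one. The day counts assume that enrolment falls on the screening day and that a month is 28 to 31 days.

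**What to change.** - **Section 4.2:** keep the existing window lengths, but count them back from the earliest assessment used as baseline, including the IVCM image. State that they also run through to enrolment, so that an exposure after the image remains excluded.
- **Section 7.1:** do not reuse earlier clinic measurements or images if any dry-eye treatment was started or changed at or after them. Repeat them at screening.
- **Case report form:** record the start or last-change date of each background dry-eye treatment, so that affected subjects can be identified.

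Repeating a test puts baseline after the new treatment has begun, but does not ensure that its effect has settled. Whether other background treatments should be stable before entry, and for how long, is for the clinical team when reconciling 4.2 with 5.2 and 5.5.

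The cost is amendment wording, one or two data fields and some repeated tests. Section 7.8 already lists these tests at the first visit, so no extra visit is created in principle. A few subjects may enrol up to about a week later.
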